PROTOCOL

Study Title: Prospective treatment study of Catatonia patients with RUL ECT and BL ECT treatment regimens

Principal Investigator, Co-investigator(s):

[name]; PI

[name]; Co-I

Sponsor or funding source: None needed specifically for the study. ECT is standard of care for catatonia and patients' insurance covers ECT treatments as a result.

Background, Rationale and Context

Catatonia was first described in 1873 by a German psychiatrist, Karl Ludwig Kahlbaum in his monograph titled "Die Katatonie oder Das Spannungsirresein" (Catatonia or tension insanity) (Kahlbaum, 1873). He conceptualized catatonia as a motor syndrome characterized by lack of motion, speech, alternating with periods of excessive purposeful motor activity, rigidity, negativism, verbigeration, automatic imbalance, posturing, grimacing and stereotypes. He also described that the syndrome generally had a periodic course and lethal outcome in a few. Despite a long history, "katatonia" was associated with different illnesses and was given as diagnostic specifier. DSM- V made a change and added catatonia as an independent diagnostic symptom.

According to DSM-V, catatonia is characterized by the following:

A. the clinical picture is dominated by 3 or more of the following symptoms
(1) Stupor (2) Catalepsy (3) Waxy flexibility (4) Mutism (5) Negativism (6) Posturing (7) Mannerism
(8) Stereotypy (9) Agitation (10) Grimacing (11) Echolalia (12) Echopraxia

B. There is evidence from the history, physical examination or laboratory findings that the disturbance is in the direct patho-physiological consequence of another medical condition.

C. The disturbance is not better explained by another mental disorder

D. the disturbance does not occur exclusively during the course of a delirium

E. The disturbance causes clinically significant distress or impairment in social, occupational or other important areas of functioning

Electroconvulsive therapy or ECT has a very good track record in treatment of catatonia (World J Psychiatr. 2015 June 22; 5(2): 182-192), but current literature does not shed light on the speed and degree of response of catatonia to ECT. This study aims to analyze and describe the change of clinical signs and symptoms as a response parameter to judge ECT treatment series efficacy.

This treatment study, will be able to compare response rate of catatonia to RUL ECT and BL ECT. Also having a control group of catatonia patients, which will not be treated with ECT will provide additional information on early ECT treatment of Katatonia.

Objectives

- Study the response rate of catatonia to right unilateral (RUL) ECT and bilateral (BL) ECT.
- Compare response rate of catatonia to RUL ECT and BL ECT
- Analyze and describe the change of clinical signs and symptoms after ECT treatment series

Methods and Measures

Design

This study is a case control study. Currently ECT is considered standard of treatment for catatonia in addition to alternative medication options.

Study participants meeting inclusion and exclusion criteria will be and providing informed consent will be randomly assigned to receive either bilateral electroconvulsive treatment (BLECT) or right unilateral electroconvulsive treatment (RULECT)

- Patients who are otherwise eligible and consent to participate in our study, but refuse ECT (or ones who are unable to consent but their court appointed legal guardian or health care power of attorney refuse ECT) will be enrolled as a control group. The control group will undergo all the same laboratory investigations and Bush Francis measurements for evaluation of their catatonia but will not receive ECT.
- Informed consent will be obtained from the study participant or their legally authorized representative by the principal investigator or sub-investigator.
- Prior to treatment each patient will be examined by a clinician (psychiatrist and psychiatric resident) in which the following information will be obtained:

- **Psychiatric interview** with uniformed questioner

- **HPI** with onset, course of presenting symptoms, comorbidities, *precipitating illness or life events – emphasis upon psychological stress*

- **Substance abuse screening**

- **Psychiatric history** – Psychiatric diagnoses with age/date of diagnoses

- **Medical history**, with focus on comorbid developments and chronic medical disease states – especially if recent worsening or change in therapy

- **Previous episodes of catatonia** – dates and pertinent developments to social history (as noted above with HPI) with time course and treatment response/failure to ECT or medications

- **Recent medication changes**, with specific focus on timing of symptoms if possible – regimen prior to symptom/sign development, medication changes, and current medication

- **Neurological conditions** – including TBI, seizure history, neurodevelopmental disorders, delirium, dementia

- The Montreal Cognitive Assessment (MOCA) will be administered the day prior to each ECT treatment and the day after each ECT treatment for pre and post procedure cognitive monitoring.

- **Incontinence**

- medical, metabolic, and/or psychiatric comorbidities are recorded but intentionally NOT excluded, with limited exceptions: CVA

- Questionnaires and rating scales: The following instruments will be administered by a trained clinician (psychiatric resident, medical student)

1) Bush- Francis Scale (BFCRS): The BFCRS is a rating scale consisting of 23 catatonia items (Bush et al., 1996a). The first 14 items on this scale are the most common, classical signs of catatonia & are also known as Catatonia Screening Instrument (BFCSI). If two or more of the BFCSI signs are present, for 24 hours or longer, catatonia is a possibility (Sienaert et al, 2011). For the purpose of this study, a score of 4 or more on the 23-item BFCRS will be considered for

inclusion in this study.

- 2) **Hamilton depression scale**
- 3) **Montreal Cognitive Assessment (MoCA)**

The administration of the BFCRS, Hamilton depression scale and MoCA will be completed before and after each ECT treatment.

- Labs and testing (to rule out organic causes of catatonia)

EEG electroencephalogram
EKG – electrocardiogram
CT scan of the head w/o contrast
CMP complete metabolic panel,
CBC diff complete blood count with differential
Thyroid studies TSH T3 T4
Metabolic/Inflammatory laboratory tests (in specific conditions)
Urine Analysis with Urine Drug Screen within 48 hours of admission)
Fe serum level
Fibrin D-dimer
–Magnesium (Mg)

- Pre-anesthesia work-up performed by the department of anesthesia to determine fitness for ECT. Anesthesia faculty will administer anesthesia to participants during the ECT procedure. They will monitor patient in the OR before, during and after the ECT procedure for at least 30 minutes for any adverse effects.
- ECT treatments will begin after initial evaluation as described above. ECT treatments will be administered three times a week.
- Participants will not be required to try and fail a challenge of IV or IM Lorazepam prior to being assigned to receive ECT treatments.

Setting

Study participants' medical histories, examinations, administration of rating scales (Bush Francis scale, MoCA and Hamilton Depression scale) will be done in the respective patient's room on the adult inpatient psychiatry unit at Wake Forest Baptist Health.

ECT treatments will be administered in OR at Wake Forest Baptist Health.

Subjects selection criteria

- **Inclusion Criteria**
- Adult patients admitted to WFBMC Inpatient Psychiatry unit with catatonia who are clinically eligible for ECT.
- Clinical catatonia as evidenced by a Bush-Francis Catatonia Rating Scale (BFCRS) score of 4 or more

- **Exclusion Criteria**

Pregnant women

Patients with any of the following medical conditions which are contraindications for ECT:

- Pheochromocytoma
- History of stroke within the past 3 months
- Cardiac conduction defects
- Cerebral or aortic aneurysms

- **Sample Size**

This study will require 30 or more to answer the questions stated in the study objectives. We will enroll 15 ECT subjects and 15 control group subjects (total sample size 30).

Interventions and Interactions

- Participants will be administered the Bush Francis Scale (BFCRS) by the principal investigator or the study coordinator the day before each ECT procedure and the day after each ECT procedure.
- Participants will receive up to 10 ECT treatments. These ECT treatments can be terminated earlier if study participants show objective clinical improvement defined as a reduction of 50% or more in the Bush Francis scale score

Outcome Measure(s)

Reduction of 50% or more in the Bush- Francis Scale (BFCRS) score.

Analytical Plan

Results will be analyzed initially using descriptive statistics. Comparison between groups will be done using chi square tests for proportions, t-tests, ANOVA procedures or other appropriate statistical analytical procedures. Regression analysis may be performed to identify independent outcome predictors. Other inferential statistical analysis will be conducted as appropriate.

Human Subjects Protection

Subject Recruitment Methods

Patients who are suffering from catatonia and hospitalized to the adult inpatient psychiatry unit will be recruited for the study. Informed consent will be obtained from patients who have capacity to make their own medical decisions and are their own legal guardians. Patients who are unable to understand the nature of their illness, the risks or benefits of accepting or refusing treatment or are unable to understand their treatment options will be determined not to have capacity to provide informed consent. In that situation, their legally appointed representative (healthcare power of attorney) or court appointment emergency legal guardian will be approached for informed consent. Informed consent will be obtained from a court appointment legal guardian for patients who have already been deemed incompetent by the court.

A trained psychiatry physician (attending psychiatrist or resident psychiatrist) will do the recruiting. Privacy will be protected by interviewing patients in the privacy of their patient room.

Informed Consent

Signed informed consent will be obtained from each subject, their legal guardian if they are deemed incompetent by a judge or their legally authorized representative if the subject is unable to provide informed consent. Informed consent will be obtained by the principal investigator or study coordinator. Informed consent will be obtained from patient or patient's legally authorized representative in

the patient's hospital room when the patient is hospitalized to the adult inpatient psychiatry unit at least a day prior to the first ECT procedure to protect patient privacy. Patient or their legally authorized representatives can rescind the consent for ECT at any time by simply verbally informing the principal investigator or study coordinator. Principal investigator will evaluate subject for capacity to consent to ECT procedure. If principal investigator determines that subject does not have capacity to consent and does not understand the risks or benefits of the ECT procedure, subject's legally authorized representative (either court appointed legal guardian or designated health care power of attorney) will be contacted for informed consent. A subject who does not have capacity and does not have a legally authorized representative or a court appointed guardian will not be enrolled in the study.

Confidentiality and Privacy

Confidentiality will be protected by collecting only information needed to assess study outcomes, minimizing to the fullest extent possible the collection of any information that could directly identify subjects, and maintaining all study information in a secure manner. To help ensure subject privacy and confidentiality, only a unique study identifier will appear on the data collection form. Any collected patient identifying information corresponding to the unique study identifier will be maintained on a linkage file, stored separately from the data. The linkage file will be kept secure, with access limited to designated study personnel. Following data collection subject identifying information will be destroyed. Identifying data will be destroyed three years after closure of the study. Data stored on paper will be shredded and videos will be deleted. Data access will be limited to study staff. Data and records will be kept locked and secured, with any computer data password protected. All study procedures will take place in the participant's hospital room with study personnel. No one other than the participant and study personnel will be allowed in the participant's hospital room when any study procedure is underway. No reference to any individual participant will appear in reports, presentations, or publications that may arise from the study.

Data and Safety Monitoring

The principal investigator will be responsible for the overall monitoring of the data and safety of study participants. The principal investigator will be assisted by other members of the study staff.

Reporting of Unanticipated Problems, Adverse Events or Deviations

Any unanticipated problems, serious and unexpected adverse events, deviations or protocol changes will be promptly reported by the principal investigator or designated member of the research team to the IRB and sponsor or appropriate government agency if appropriate. Adverse Events will be collected and assessed for relationship for ECT treatments on ECT subjects only.

References

1. Kahlbaum KL. Die Katatonie: oder das Spannungsirresein, eine klinische Form psychischer Krankheit. 1973
2. World J Psychiatr. 2015 June 22; 5(2): 182-192.
3. Bush, G., Fink, M., Petrides, G., Dowling, F., Francis, A., 1996a. Catatonia. I. Rating scale and standardized examination. Acta Psychiatr. Scand. 93, 129–136.

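### The change seen within the ECT arms is to be used to judge efficacy, but only RUL versus BL is randomised and the sole no-ECT reference is 15 patients for whom ECT was refused

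*Combined protocol and SAP*

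**What the plan says.** - **Aim (Background, Rationale and Context).** The study will analyse and describe the "change of clinical signs and symptoms as a response parameter to judge ECT treatment series efficacy". The same section reports, from the historical description of catatonia, that "the syndrome generally had a periodic course".
- **Objectives.** The first is the response rate to RUL ECT and to BL ECT. The second compares the two. The third is to "Analyze and describe the change of clinical signs and symptoms after ECT treatment series". None names a no-ECT comparator.
- **Allocation (Design).** Consenting participants are "randomly assigned to receive either bilateral electroconvulsive treatment (BLECT) or right unilateral electroconvulsive treatment (RULECT").
- **Control group (end of Background; Design).** The rationale says that "having a control group of catatonia patients, which will not be treated with ECT will provide additional information on early ECT treatment". Its members are "Patients who are otherwise eligible and consent to participate in our study, but refuse ECT", or patients lacking capacity whose guardian or health care proxy refuses it. On measurement: "The control group will undergo all the same laboratory investigations and Bush Francis measurements for evaluation of their catatonia but will not receive ECT".
- **Rating times (Interventions and Interactions).** The BFCRS is given "the day before each ECT procedure and the day after each ECT procedure". No calendar schedule is given for controls.
- **Size, outcome and analysis.** There are 15 ECT and 15 control subjects. The outcome is a fall of at least 50% in BFCRS, with no fixed time point. The Analytical Plan names chi-square tests, t-tests and ANOVA between groups, without saying which groups, and optional regression without naming covariates.

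**The concern.** The Background gives the description of change a purpose, which is to judge whether the ECT series works. As the objectives are written, the figures that would serve that purpose are the response rate and the change in treated patients. These patients enter while symptomatic (BFCRS of 4 or more), have an illness described as periodic, and may be on medication that the protocol does not restrict. Some would improve without ECT.

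If most patients in both arms reach the 50% fall, the report could present RUL and BL as each efficacious. The randomised comparison could show at most that one placement does better or worse than the other. Two arms with equally high response are compatible with two equally effective treatments, and also with a favourable course common to both.

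**Working it through.** **1. What each comparison can support**

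| Comparison | Assignment | Listed objective? | What it supports |
|---|---|---|---|
| RUL versus BL | Randomised | Yes (second) | Relative effect of placement |
| Before versus after, within ECT arms | None | Yes (first and third) | Description of course during ECT |
| ECT versus no ECT | Refusal by patient or representative | No | Observational contrast, open to confounding |

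The efficacy of an ECT series is a question for the third row. The objectives address only the first two.

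**2. The plan's own figure.** 15 ECT + 15 control = 30, which agrees with the stated total. No significance level, power or response rate is given, so the size cannot be reproduced from a calculation.

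**3. What a within-arm rate tells us.** Suppose 12 of 15 ECT patients respond (assumed). The exact 95% interval is 52% to 96%. It describes response during ECT and carries no information on response without it.

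**4. What the control group could add.** Assume 15 versus 15, two-sided 5%, and 80% response on ECT. With p the mean of the two rates, normal-approximation power = Φ{[|p1 − p2|√n − 1.96√(2p(1 − p))] / √[p1(1 − p1) + p2(1 − p2)]}. For 80% versus 30%: (0.5 × 3.873 − 1.96 × 0.704) / 0.608 = 0.92, so power is 82%.

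| Control response (assumed) | Normal approximation | Fisher exact |
|---|---|---|
| 30% | 82% | 68% |
| 40% | 62% | 45% |
| 50% | 40% | 25% |

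So the group can show a large difference, but not reliably a moderate one.

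**5. What refusal could do to that contrast.** Assume no ECT effect, with 50% falls in 70% of good-prognosis and 20% of poor-prognosis patients. If 60% of ECT patients and 40% of controls have a good prognosis, the rates are 0.6 × 0.7 + 0.4 × 0.2 = 50% and 0.4 × 0.7 + 0.6 × 0.2 = 40%, a false difference of 10 points. A 70/30 split gives 55% − 35% = 20 points, and an 80/20 split gives 60% − 30% = 30 points. The bias could also run the other way. The documents do not say how refusers differ.

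**6. Background response, as an illustration only.** Ten treatments on Monday, Wednesday and Friday, rated the day before and the day after each, give a baseline and 13 later rating days. I simulated 60,000 trendless lognormal courses per setting, with mean 14, day-to-day autocorrelation 0.3-0.8 and no ECT effect. All these values are assumptions. The table shows the proportion with a fall of at least 50% from baseline.

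| Day-to-day CV | Any later rating, unrounded | Any later rating, integer scores | Last rating (either) |
|---|---|---|---|
| 20% | 3-5% | 4-7% | about 1% |
| 30% | 18-26% | 20-30% | 5-6% |
| 40% | 33-44% | 36-48% | 10-11% |
| 50% | 45-56% | 47-59% | 15-16% |

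The model has no remission, no episodes, no medication effect and no selection at a symptomatic peak. It therefore measures rating noise over repeated looks and does not estimate natural course.

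**The case against.** The strongest reply is that this is not a before-after study. Half the planned sample is a concurrent group of otherwise eligible patients with the same BFCRS measurements and no ECT. They enter under the same threshold, so regression to the mean affects them too, and the Analytical Plan provides for comparison between groups. A reader might infer from the randomisation alone that ECT effect and natural course cannot be separated at all, and that any efficacy conclusion has no support. The documents do not bear that out, because a no-ECT reference exists. What can be said is that it is small, selected by refusal, tied to no listed objective, without a rating schedule of its own, and without named covariates.

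Second, the aim is partly descriptive. The sentence speaks of analysing and describing, the third objective repeats this, and the Background treats ECT as already having a good record in catatonia and names speed and degree of response as the gap. A reader might infer that the sponsor will declare each placement efficacious against no treatment, but no section says so. This part of the objection narrows the point without removing it, because the sentence still ends in judging efficacy.

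Third, the simulated rates depend on inputs that are not in the documents, and day-to-day noise is not natural course. That stands. Quoting only the upper rates, or turning them into a share of an assumed ECT response, would be selective.

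**Conclusion.** The concern holds in a limited form. An efficacy conclusion drawn from change within the ECT arms is not supported by the randomised comparison, which concerns placement only. It is only weakly informed by 15 non-randomised controls for whom ECT was refused. The randomised RUL-versus-BL objective is not affected by this point.

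This conclusion rests on the text of the aim, the objectives and the allocation, and needs no numerical assumption. Its size cannot be derived from the documents. The simulated background rates (about 1-16% at a last rating, 3-59% at any rating, for a CV of 20-50%) and the false differences of 10-30 points show what assumed inputs would produce and are not estimates for this trial. The wording should be corrected before analysis. The defect lies in the claim attached to the data and does not make the data unusable.

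**What to change.** 1. **Background.** Replace the closing purpose of the aim sentence, on judging efficacy, with 'to describe the course of signs and symptoms during an ECT series'.
2. **Objectives.** Word the first objective as the proportion with a BFCRS reduction of 50% or greater during RUL ECT and during BL ECT.
3. **Analytical Plan.** Add three statements:
   - Within-arm change is descriptive and will not be reported as the effect of ECT.
   - Randomised inference is limited to RUL versus BL.
   - Any ECT-versus-control comparison will be labelled observational and adjusted for baseline BFCRS, with control ratings read at calendar days matched to the ECT course.

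Adjusting for baseline BFCRS will not remove confounding by the reasons for refusal, and the report should say so.

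**Cost.** Wording in three places, a less favourable efficacy claim and a little more analysis work. No additional patients are needed, and no treatment changes. Controls are already due the same BFCRS measurements, so what is added for them is a defined set of days.

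### ECT versus control is a non-randomised contrast with no planned adjustment and no common end time, because controls are patients who decline ECT and follow-up BFCRS ratings are timed by ECT sessions

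*Combined protocol and SAP*

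**What the plan says.** Under Methods and Measures, Design, the protocol states "This study is a case control study". Participants who accept ECT are randomised between bilateral and right unilateral treatment. The control group is "Patients who are otherwise eligible and consent to participate in our study, but refuse ECT", with the same rule when a guardian or health care proxy refuses.

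The three listed objectives concern RUL and BL ECT and the change in signs after an ECT series. None compares ECT with no ECT. The Background, however, says that "having a control group of catatonia patients, which will not be treated with ECT will provide additional information on early ECT treatment of Katatonia", and Sample Size assigns 15 patients to ECT and 15 to control.

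On treatment, the Design section says: "Currently ECT is considered standard of treatment for catatonia in addition to alternative medication options". Medication appears in the pre-treatment examination ("regimen prior to symptom/sign development, medication changes, and current medication"), as does the history of earlier episodes ("with time course and treatment response/failure to ECT or medications"). No medication record during follow-up is described.

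On timing, Design says of controls: "The control group will undergo all the same laboratory investigations and Bush Francis measurements". The rating scales "will be completed before and after each ECT treatment". Interventions and Interactions places the BFCRS on the day before and the day after each procedure, and allows ECT to stop early once the score has fallen by 50% or more. The outcome is that same 50% reduction, with no day attached.

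The Analytical Plan lists chi-square tests, t-tests, ANOVA or other suitable procedures for comparing groups that it does not define. It adds that regression may be used to look for outcome predictors.

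**The concern.** Patients who decline ECT may differ from those who accept it in severity, negativism, capacity, earlier response to ECT or other treatment. The documents do not say that they do, but nothing in the design prevents it and nothing in the analysis deals with it. Controls are also non-ECT rather than untreated patients, and what they receive during follow-up would go unrecorded.

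Timing is a separate problem. A literal reading of the schedule gives a control patient no rating after inclusion. In the ECT group, the last rating depends on the outcome itself, because treatment can end on response. If the two groups are last rated on different days, their response rates differ even when the illness runs the same course.

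At stake is what the control half of the sample can show. A difference, or the lack of one, could reflect who refused, what else they received, or when they were rated. Rating days and medication records cannot be recovered at the analysis stage.

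**Working it through.** **Inputs from the documents.** 15 ECT and 15 control patients; response is a BFCRS reduction of 50% or more; up to 10 sessions, three a week. No significance level, power, response rate or dropout is given. The plan therefore has no figure on this point to reproduce, and the total of 30 cannot be re-derived. Everything below assumes a two-sided 5% level and assumed response rates.

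**1. Selection, no ECT effect.** Let responders be X ~ Bin(15, p1) among acceptors and Y ~ Bin(15, p2) among refusers. The rejection rate is the sum of P(X=x)·P(Y=y) over all 15-versus-15 tables that the test calls significant.

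| Assumed response, acceptors/refusers | Uncorrected chi-square | Fisher's exact |
|---|---|---|
| 50/50 | 4.6% | 1.7% |
| 50/40 | 7.9% | 3.3% |
| 50/30 | 19.5% | 9.7% |
| 60/30 | 37.0% | 22.7% |

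**2. The opposite direction.** Suppose ECT raises response from 30% to 60% in acceptors. If refusers would respond at 30% on non-ECT care, the uncorrected chi-square detects the difference in 37% of trials. If refusers would respond at 50%, the comparison is 60 versus 50 and detection falls to 8% (Fisher: 23% to 3%).

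**3. Timing alone.** Assume the same course in both groups, with 50% responding by day 23 at a constant hazard and response lasting. A control last rated on day d then shows 1 − 0.5^(d/23).
- d = 14: 34%; rejection against 50% is 13.2% (chi-square) or 6.1% (Fisher).
- d = 7: 19%; rejection is 44.6% or 26.7%.

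Controls rated later than ECT patients would give bias of the opposite sign.

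**4. What adjustment can do.** This was a simulation with no ECT effect, 2,500 trials per case, and a Firth penalised likelihood-ratio test adjusted for baseline BFCRS. If baseline BFCRS carries half of the prognostic gap, rejection is 8–9% (50/30) and 12–15% (60/30). If it carries a quarter, rejection is 12–13% and 21–25%. The fair reference is the uncorrected 20% and 37%, not the more conservative Fisher figures. Adjustment reduces the bias but does not remove it.

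**5. Precision.** For 50% versus 30%, the 95% CI half-width is 1.96·√(0.5·0.5/15 + 0.3·0.7/15) = 0.343, or about ±34 points.

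**6. Calendar.** On an assumed Monday/Wednesday/Friday pattern, session 10 falls 21 days after session 1, and the last rating one day later. If session 1 is D days after the inclusion rating, the last rating of a full course is on day D + 21 + 1 = 22 + D: day 23 for D = 1, day 29 for D = 7.

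**The case against.** The strongest reply is that ECT versus control is not a listed objective, and the groups in the Analytical Plan could mean RUL and BL only. That limits the weight of the point but does not remove it. Half the sample is control, the Background gives that group a purpose, and no other analysis is assigned to it.

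A second reply is that the clause on other suitable procedures, together with the optional regression, already allows adjustment. It allows it, but names no covariate and no contrast, so nothing is prespecified.

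A third is that controls are promised the same Bush-Francis measurements, which may simply be a matched schedule that is poorly worded. This is fair as to intent. The inclusion BFCRS also gives both groups a common starting reading. What is missing is control rating days and a common end time.

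Three stronger readings are tempting, and the documents support none of them:
- A reader might infer that the comparison must exceed its 5% level whenever refusers differ in prognosis. It need not: at 50/40, Fisher's exact test rejects in 3.3%, and the plan does not say which test will be used.
- A reader might infer that controls will be rated earlier than ECT patients. Nothing says so; days 7 and 14 are illustrations.
- A reader might infer that the whole trial is confounded. Refusal happens outside the randomised groups.

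**Conclusion.** The point holds and should be fixed. ECT versus control is a non-randomised contrast that the case-control label misdescribes, with no prespecified adjustment, no record of co-treatment during follow-up and no common end time. An unadjusted comparison can be biased towards or away from ECT.

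The size cannot be taken from the documents. Under the assumed rates and no ECT effect, rejection runs from 8% to 37% (uncorrected chi-square) or 3% to 23% (Fisher), against 5% and 2% with no prognostic difference. These figures show sensitivity to the assumptions and are not forecasts. That refusal tracks prognosis is plausible but is also an assumption.

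The randomised RUL-versus-BL comparison is not affected by refusal, so the point concerns only what may be claimed from the control group.

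**What to change.** 1. **Design wording.** Describe a randomised RUL-versus-BL comparison plus a concurrent non-randomised cohort declining ECT (non-ECT, not untreated). Analyse RUL versus BL in randomised patients only.
2. **ECT versus non-ECT.** Report it as exploratory and non-randomised, adjusted for inclusion BFCRS (for example by penalised logistic regression), with a 95% CI. Add a baseline table by group that includes prior ECT response and current medication. Record medication in all groups during follow-up. State that residual confounding remains.
3. **Timing.** Take the inclusion BFCRS as the index reading in every group. Give controls calendar rating days that mirror the three-per-week session schedule. Name one common day, checked against 22 + D, and compare response by that day using each patient's last inpatient BFCRS on or before it.
4. **Early discharge.** Do not set patients discharged before the common day to missing in the main analysis. ECT can stop on response and ratings are made on the inpatient unit, so missingness would then depend on outcome. Add one sensitivity analysis restricted to patients rated on the day, and one with both extreme assumptions. With 3 of 15 unrated per group (assumed), the extremes lie 2·3/15 = 40 points apart; with 6 of 15, 80 points.
5. **End-of-series response.** Report it separately, in ECT patients only.

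**Cost.** Protocol and analysis wording; control ratings that the plan already intends, now with dates; up to one common-day rating per ECT patient; and a medication record. The main analysis relies on last ratings for patients discharged early, and the claim from the control group becomes weaker.
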